1.1 How will you define adverse events (AE)) for this study?

X An adverse event will be considered any undesirable sign, symptom or medical or psychological condition **even if the event is not considered to be related** to the investigational drug/device/intervention. Medical condition/diseases present before starting the investigational drug/intervention will be considered adverse events only if they worsen after starting study treatment/intervention. An adverse event is also any undesirable and unintended effect of research occurring in human subjects as a result of the collection of identifiable private information under the research. Adverse events also include any problems associated with the use of an investigational device that adversely affects the rights, safety or welfare of subjects.

1.2 How will you define serious adverse events?

X A serious adverse event will be considered any undesirable sign, symptom, or medical condition which is fatal, is life-threatening, requires or prolongs inpatient hospitalization, results in persistent or significant disability/incapacity, constitutes a congenital anomaly or birth defect, is medically significant and which the investigator regards as serious based on appropriate medical judgment. An important medical event is any AE that may not result in death, be life-threatening, or require hospitalization but may be considered an SAE when, based upon appropriate medical judgment, it may jeopardize the patient and may require medical or surgical intervention to prevent one of the outcomes listed in the definitions of SAEs.

1.3 What is the definition of an unanticipated problem?

Do not change this answer

An unanticipated problem is any event, experience that meets ALL 3 criteria below:

- Is unexpected in terms of nature, severity or frequency given the research procedures that are described in the protocol-related documents AND in the characteristics of the subject population being studies
- Related or possibly related to participation in research. This means that there is a reasonable
 possibility that the incident may have been caused by the procedures involved in the research
 study.
- The incident suggests that the research placed the subject or others at greater risk of harm than was previously known or recognized OR results in actual harm to the subject or others

Page 30 of 50

1.4	What	is the	definition	of a	protocol	violation?	,
-----	------	--------	------------	------	----------	------------	---

Do not change this answer

A protocol violation is defined as any change, deviation, or departure from the study design or procedures of a research project that is NOT approved by the IRB-HSR prior to its initiation or implementation, OR deviation from standard operating procedures, Good Clinical Practices (GCPs), federal, state or local regulations. Protocol violations may or may not be under the control of the study team or UVa staff. These protocol violations may be major or minor violations.

Additional Information: see the IRB-HSR website at http://www.virginia.edu/vpr/irb/HSR_docs/Forms/Protocol_Violations_%20Enrollment_Exceptions Instructions.doc

1.5	If pregnancy occurs how will this information be managed? Female subjects know that
	pregnancy is an exclusion criteria for participation in this study. An HCG screen will also be done
	before virus inoculation and subjects excluded if the test is positive. During the 3 weeks of
	monitoring during the cold, we will not know if the subjects become pregnant, but this is unlikely
	and there is no reason to believe that the experimental rhinovirus infection will have any adverse
	effects on the fetus different from a natural cold.
	Adverse Event- will follow adverse event recording and reporting procedures outlined in section 3.
	section 3.
	Unanticipated Problems- will follow Unanticipated Problem recording and reporting
	procedures outlined in section 3.
	X Other- will follow op to obtain outcome information that will be documented in the source
	documents in the subject's study binder
1.6	What is the definition of a Protocol Enrollment Exception?
	X_NA- No outside sponsor

1.7 What is the definition of a data breach?

Do not change this answer

A data breach is defined in the HITECH Act (43 USC 17932) as an unauthorized acquisition, access, or use of protected health information (PHI) that compromises the security or privacy of such information.

Additional Information may be found on the IRB-HSR Website: Data Breach

2. Identified risks and plans to minimize risk

2.1 What risks are expected due to the intervention in this protocol?

Expected Risks related to study participation.	Frequency
Viral Inoculation	
Cold Symptoms	X Occurs frequently

Page 31 of 50

Mild wheezing	Occurs infrequently		
Chest tightness	Occurs rarely		
Chest tightness	Frequency unknown		
Warganing agthma gymntams	X Occurs frequently, although mild		
Worsening asthma symptoms	Occurs infrequently		
	Occurs rarely		
	Frequency unknown		
Other risks:	V. O. array in fragmental and the fragmental and th		
	X Occurs infrequently (uncommon in		
Rhinovirus infections may	experimental colds)		
infrequently be associated with			
ear infections or sinus infections.			
Ear infections cause ear pain			
(earache) and sinusitis [an			
inflammation of the sinuses			
(hollow spaces in the bone of the			
cheeks and forehead) due to an			
infection] may cause sinus			
pressure or pain. These			
complications have been			
uncommon in volunteers			
experimentally infected with			
rhinovirus. If these infections			
develop they can be treated with			
antibiotics. If antibiotics are			
required the PI will prescribe the			
antibiotics but you will be			
responsible for buying the			
antibiotics.			
	W O : C		
A transient decline in blood cells	X Occurs infrequently.		
(neutrophils) which are used to			
fight bacterial infections is			
common, but serious declines			
below 1000 cells/mm3 or serious			
sinus infections linked to			
infections with the common cold			
virus (rhinovirus) are uncommon	X Rare. This problem has never occurred.		
and have not yet been observed.	Trace, this protein has never occarred.		
 Serious bacterial infections (such 	X Rare. This problem has never occurred.		
as pneumonia).	1		
• The virus that will be used for			
the study is a rhinovirus that was			
isolated from a volunteer in a			
previous study. The donor			
volunteer was tested for HIV			
(AIDS), hepatitis C, and			

hepatitis B infection and found	
to be negative. After isolation,	
the virus was tested for the	
presence of other germs	
associated with infections in	
humans. Although none were	
found there is a remote chance	
that an unknown pathogen could	
be present and cause infection.	
This problem, however, has	
never occurred. The safety	
testing done on this virus has	
been reviewed by the FDA and	
the FDA has given us permission	
to use the virus for these	
experimental studies.	
Distance Continue to the conti	
Risks of Spirometry Dizziness	0 0 1
	Occurs frequently
Coughing	_XOccurs infrequently
	Occurs rarely
	Frequency unknown
CI (CI (I	0 0 1
Shortness of breath	Occurs frequently
Mild respiratory fatigue	_X_Occurs infrequently
Chest tightness	Occurs rarely
Chest soreness	Frequency unknown
Fainting	
Methacholine Challenge Testing	
Chest tightness	X_Occurs frequently
Cough	Occurs infrequently
	Occurs rarely
	Frequency unknown
Dyspnea	Occurs frequently
Wheezing	_X_Occurs infrequently
Lightheadedness	Occurs rarely
Increased respiratory secretions	Frequency unknown
Pruritis	
Headache	
Throat Irritation	
Difficulty breathing	Occurs frequently
	Occurs infrequently
	X_Occurs rarely
	Frequency unknown
Severe asthma attack during testing	X_Occurs rarely
D'I CAU I	
Risks of Albuterol	
Mild throat irritation	Occurs frequently X Occurs infrequently
Cough	A Occurs infreduentiv

Page 33 of 50

Increased pulse rate	Occurs rarely
Mild tremor	Frequency unknown
Headache	
Dizziness	
Insomnia	
Sweating	
Nausea	
Vomiting	
Dry Mouth	
Allergic Reaction	Occurs frequently
Chest pain	Occurs infrequently
	_X_Occurs rarely
	Frequency unknown
Risks of Nasal Wash	
Coughing	_ Occurs frequently
Nasal Irritation	$\frac{\overline{X}}{X}$ Occurs infrequently
	Occurs rarely
	Frequency unknown
	1
Monitoring of nasal mucous weights	No risk,
D' L CE L LINY O' L	X Occurs infrequently
Risks of Exhaled Nitrous Oxide	
Feeling of light headedness if subjects	
blow to hard	
Risks of Sterile Surgicel Guaze (1 X 1	X Mild to moderate irritation occurs frequently
cm) Applications to the Nasal Inferior	and resolves quickly
Turbinates to collect Nasal Lining	X Sneezing occurs occassionally
Fluid	
Mild to moderate irritation	
Sneezing	V 0 'C 4 / 1 '4 ' 1 1 1
Impulse Oscillometry	X Occurs infrequently (reversed with inhaled
Mild light-headedness and coughing,	albuterol).
shortness of breath, and/or chest tightness.	
Phlebotomy	
, , , , , , , , , , , , , , , , , , ,	X Occurs frequently
	Occurs infrequently
Phlebotomy: local discomfort and bruising	Occurs rarely
	Frequency unknown
	Occurs frequently
	Occurs infrequently Occurs infrequently
Phlahotomy: vacovagal ranations	X Occurs rarely
Phlebotomy: vasovagal reactions	Frequency unknown
	rrequency unknown
Risks of ASI Rhino-Pro ® sampling	
Tingling	Occurs frequently
Sneezing	X Occurs infrequently; the procedure takes
	30 seconds.
Epstaxis (easily stopped using standard	
treatment – i.e., applying pressure to the	Occurs rarely
outside of the nose)	Frequency unknown

Page 34 of 50

Nose bleed	Occurs frequently Cocurs infrequently X Occurs rarely Frequency unknown
Nasal Bleeding	Occurs frequentlyOccurs infrequentlyX_Occurs rarely Frequency unknown

3.2 List by bullet format a summary of safety tests/procedures/observations to be performed.

- Adequate screening including Pregnancy Testing
- Pulse Oximetry (should symptom exacerbations occur as noted in the Treatment Plan above, pg. 13)
- Physical Exams
- Spirometry
- Daily home symptom and FEV₁ monitoring.
- Physicians and/or nurses, or respiratory therapists from the University of Virginia Asthma and
 Allergic Diseases Center, or the Pediatric Respiratory Disease division will be on site in the hotel
 24/day for the duration of the subjects' hotel stay. The study team on site will provide monitoring of
 the study subjects and will be available as needed to the study subjects. In addition, epinephrine,
 albuterol, and oral steroids will be readily available to the member of the study team to use for
 treatment if necessary.

2.3 Under what criteria would an INDIVIDUAL SUBJECT'S study treatment or study participation be stopped or modified X At subject, PI or sponsor's request

V C(1 1 11 ('C(1 1' (1 1 ' 1 1

__X__Study procedures would stop if the subject had a serious adverse event deemed related to the study. See description of SAE's above..

X If, after inoculation with the RV-16 pool, two subjects experience severe asthma exacerbations requiring oral steroids for ≥ 5 days annually (during the spring or fall enrollments), or if 1 subject requires treatment in the ER with systemic steroids, or hospitalization at any time during the study. Among the last 46 asthmatic subjects challenged with RV, only one subject required intervention with a 5 day course of oral steroids, but did not require treatment in the ER or hospitalization (which has never occurred in our rhinovirus challenge studies). Because the exclusion criteria (see below) obviates the enrollment of subjects who have required treatment in the ER, or hospitalization during the last 3 years (or any intubation ever requiring management in an intensive care unit), we suspect that it is not likely that the above stopping rules will be encountered.

Page 35 of 50

X If 2 subjects developed a significant lower tract infection (not including bronchitis) following RV-16 inoculation and this will lead to stopping the study for further review. Lower respiratory tract infections have not yet occurred during experimental (or even natural) infections with rhinovirus in an immune competent host, because this pathogen is not known to be a cause of pneumonia. It is conceivable, however, that one or two subjects could acquire another respiratory tract pathogen that could cause a lower respiratory tract infection.

X An absolute neutrophil count < 1000 cells/mm3 detected in CBC and differential cell counts at any time during the study.

X A blood hemoglobin level < 10.0 g/dL detected in CBC and differential cell count at any time during the study, in keeping with a NCI-CTCAE grade one adverse event.

X Death: One death will lead to stopping the study until an expedited review is completed to determine whether the death might have resulted from any of the study procedures.

2.4 Under what criteria would THE ENTIRE STUDY need to be stopped. _X_ Per IRB, PI, DSMB, or sponsor discretion
_XOther: This study would also be stopped if more than two subjects required oral steroids for asthma symptoms following RV inoculation, or if more than one emergency room visit or hospitalization occurred. Thus far, no emergency room or hospitalizations have occurred in our studies and none, that we are aware of, have been described in the literature.

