- Review diaries at every visit and issue new diaries at Days 7 and 14

Study Visit Day 28 - Subjects will complete the Asthma Control Test to summarize their symptoms since the day of virus inoculation (Day 0) and pick up their check for study payment. Note: This study visit can be completed one day before or one day afterward, although completing the Asthma Control Test on day 28 following virus inoculation is strongly encouraged.

Treatment guidelines should symptom exacerbations occur during the study:

If a study participant experiences an increase in lower respiratory tract symptoms, or a decline in lung function, the following plan describes how subjects will be treated.

[figure not shown]
- For FEV1 value dropping between 20-29% from the baseline value not responding to albuterol, start on inhaled corticosteroids (Flovent 110 mcg./puff, 2 puffs bid) and discontinue when symptoms return to baseline.
- For FEV1 value dropping between 30-49% from the baseline value not responding to albuterol, check oximetry and start on inhaled corticosteroid as above and 3 to 5 days of oral steroids (Prednisone 50 mg/day).
- For FEV1value dropping 50% or more from the baseline value. Transportation to the emergency room will be recommended and arranged. Individual stopping rules will apply as described in the Complete Clinical Protocol (Section 8.1.2). Further follow-up and management with the subject's primary care doctor; [name] and his study team will continue to be involved and available for follow-up and evaluation 30 days afterward for any subject who requires oral steroids, a visit to the ER, or hospital admission.

Page 19 of 50

Further follow-up and management with the subject's primary care doctor, [name], and his study team will continue to be available for follow-up and management 30 days afterward for any subject who requires oral steroids, a visit to the ER, or hospital admission.

These treatment plans are in keeping with recommendations from the Guidelines for the Diagnosis and Management of Asthma (16)

DIAGRAM: EXPERIMENTAL RHINOVIRUS STUDY DESIGN

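### Sections 2.3 and 2.4 set inconsistent cross-subject stopping thresholds, and the plan does not say what follows when the lower one is met first

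*Combined protocol and SAP*

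**What the plan says.** Two adjacent items of the Data and Safety Monitoring Plan carry numerical stopping criteria for asthma events.

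The heading of the first reads "2.3 Under what criteria would an INDIVIDUAL SUBJECT'S study treatment or study participation be stopped or modified". One bullet beneath it has two limbs. The steroid limb is met when "two subjects experience severe asthma exacerbations requiring oral steroids for ≥ 5 days annually"; a parenthesis ties this count to the two enrolment seasons. The other limb, for emergency or hospital care, is met "if 1 subject requires treatment in the ER with systemic steroids, or hospitalization at any time during the study". The bullet gives no consequence for either limb. It ends by saying "we suspect that it is not likely that the above stopping rules will be encountered".

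Section 2.4, on stopping the entire study, first allows stopping at the discretion of the IRB, investigator, DSMB or sponsor. It then sets a steroid count: "This study would also be stopped if more than two subjects required oral steroids for asthma symptoms following RV inoculation". Its alternative condition, for emergency or hospital care, reads "or if more than one emergency room visit or hospitalization occurred".

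The treatment guidelines for exacerbations provide, for one band of FEV1 decline, "3 to 5 days of oral steroids" with inhaled corticosteroid. For the largest decline they refer to individual stopping rules in Section 8.1.2 of a Complete Clinical Protocol, which is not among the documents available here.

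**The concern.** Asthmatic volunteers are deliberately infected and have no direct benefit, so the point at which further inoculation must stop should be readable in only one way. Here the lower counts (two, and one) stand under a heading about single subjects with no action attached. The higher counts (more than two, and more than one) stand under the heading about the whole study. The lower counts would be reached first, and at that moment the investigator and the Safety Monitoring Committee could each cite a section in support of a different response to the same event. The two sections also count different things, so simply applying the lower number does not settle the matter.

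**Working it through.** The documents give no operating characteristics for either rule, so there is no stated figure to reproduce.

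**Step 1: the two texts side by side.**

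| | Section 2.3 | Section 2.4 |
|---|---|---|
| Heading | individual subject | entire study |
| Steroid count | 2 subjects | more than 2 subjects, i.e. at least 3 |
| Steroid event | severe exacerbation, oral steroids for 5 days or more | any oral steroids for asthma symptoms |
| Time unit for steroid count | annual | none |
| ER/hospital count | 1 subject | more than 1 event, i.e. at least 2 |
| ER event | treatment with systemic steroids | any visit |
| Consequence | not stated | study stopped |

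**Step 2: is the 2.3 bullet a rule about the study?** It cannot operate on one person, because it counts two subjects in a year. It calls its own criteria stopping rules. Two other bullets in 2.3, on two lower respiratory tract infections and on one death, expressly stop the study pending review. A separate 2.3 bullet already covers a related serious adverse event in a single subject. Study-level intent is therefore a strong inference, but it remains an inference.

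**Step 3: where the rules differ.** Treat each event as meeting both definitions and falling in one year. Let s be the steroid subjects (0 to 3) and e the ER/hospital events (0 to 2). Rule 2.3 is met if s ≥ 2 or e ≥ 1; rule 2.4 is met if s ≥ 3 or e ≥ 2. Of the 4 × 3 = 12 combinations, four meet 2.3 but not 2.4: (s, e) = (0,1), (1,1), (2,0) and (2,1).

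**Step 4: are the rules nested?** No. Three subjects given 3- or 4-day courses, which the treatment guidelines allow, meet the 2.4 steroid limb and not the 2.3 steroid limb. Three 5-day courses in three different years also meet 2.4 and not 2.3. So do two ER visits without systemic steroids.

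**Step 5: illustrative size.** Inputs: 18 asthmatics (Study Synopsis); one oral-steroid course among the last 46 asthmatics challenged (section 2.3), so p = 1/46; independent events.

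- Pooled, at least 2: 1 − (45/46)^18 − 18(1/46)(45/46)^17 = 1 − 0.6733 − 0.2693 = 0.0574, or 5.7%.
- Pooled, at least 3: subtract P(exactly 2) = 0.0509, leaving 0.0066 after rounding, or 0.7%.
- The 2.3 count is annual and the Synopsis gives 60 months. With assumed enrolment of 9 + 9 over two years, P(at least 2 of 9) = 0.01537, so P(met in some year) = 1 − (1 − 0.01537)² = 3.1%.
- With 6 + 6 + 6: 1 − (1 − 0.00669)³ = 2.0%.
- With 4, 4, 4, 3, 3 over five years: 1 − (1 − 0.002754)³(1 − 0.001397)² = 1.1%.
- ER/hospital: the protocol reports no such events, so 1% is an assumption. At least 1: 1 − 0.99^18 = 16.5%. At least 2: subtract 18(0.01)(0.99)^17 = 0.1517, leaving 1.4%.

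One rate does not truly serve both steroid definitions. The 1/46 describes a 5-day course, whereas 2.4 counts a course of any length.

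**The case against.** A reader might infer that the sections flatly contradict each other, with 2.3 ordering a stop and 2.4 ordering continuation. The text does not go that far. Section 2.4 never says to continue below its counts; it gives sufficient conditions and also permits discretionary stopping. Both sections could be obeyed by stopping whenever either is met. That point stands. On that reading, though, the hospitalization part of 2.4 would be redundant, and 2.3 would need a consequence it does not state.

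A second defence is a two-tier scheme: 2.3 triggers a pause and review, and 2.4 a full stop. The thresholds are one step apart, and the neighbouring infection and death bullets do describe a pause. The scheme is plausible, but nothing states it for asthma events.

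Third, the Complete Clinical Protocol might settle the hierarchy. It cannot be checked here, which limits how firmly one can call the boundary undefined.

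Fourth, a first admission would not pass unreviewed. Hospitalization makes an event serious, and a related serious event stops that subject's procedures. Serious unexpected events go to the NIAID Medical Officer within 1 calendar day and to the IRB within 7, and a Safety Monitoring Committee oversees the study. All of this stands, but none of it supplies a study-level count.

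Finally, it is tempting to quote 5.7% against 0.7% as the gap between the two steroid rules. That comparison ignores the annual count in 2.3 and the different event definitions, so it is not a model of the rules as written.

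**Conclusion.** The concern holds as an inconsistency in safety thresholds that needs correction, not as proof of opposite instructions. When the first hospitalization occurs, or the second qualifying steroid case within a year, 2.3 is met, the numeric rule in 2.4 is not, and the available documents do not name the resulting action. The differences in event definition and time unit are plain on the page and depend on no assumed rate. The study-level reading of 2.3 is inferred from its wording and its neighbouring bullets.

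The probabilities only indicate scale. They rest on 18 asthmatics, independence, a rate from one event in 46, assumed yearly enrolment and an assumed 1% ER/hospital rate. Within those limits, the chance of meeting the lower steroid count is a few per cent at most under the annual reading, and the ER/hospital limb is where the two thresholds differ most. The population is itself unsettled: the protocol speaks of 36 new subjects and of 74 in total. If 2.4 counts the whole protocol, the asthmatics number 21 + 18 = 39.

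**What to change.** The sponsor and the Safety Monitoring Committee should reconcile sections 2.3 and 2.4 and check the result against the Complete Clinical Protocol section cited in the treatment guidelines. Specifically:

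- Move all cross-subject counts out of 2.3, leaving only single-subject criteria there.
- For each count, define the countable event, including how steroid courses shorter than 5 days and ER visits without systemic steroids are treated.
- State the time unit: calendar year, enrolment season or whole study.
- State the population counted: the 36 new subjects or all 74.
- State the consequence: pause for review, and by whom, or stop.

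The thresholds are for the sponsor and committee to choose; none is proposed here. The cost is amendment wording and its review, with no added procedures or data collection.
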